4.3. Type and Number of Subjects

Approximately 25 subjects will be randomised such that approximately 20 evaluable subjects complete the study. Eleven subjects were enrolled into Part 1 of the study (before the first interim analysis), and up to 14 subjects will be enrolled into Part 2 of the study. The target of 20 evaluable subjects may be revised following the sample size re-estimation, see Section 9.2.2.

If subjects prematurely discontinue the study, additional replacement subjects will not be recruited in order to preserve randomisation integrity.

4.4. Design Justification

The study design is based on a paper published by [Ricart](#), 2005 and is considered to be feasible. The study will provide important information on whether GSK2586881 modulates the acute HPV response in healthy volunteers. In addition, the study will include assessments of PK and PD effects of GSK2586881. This will be achieved by assessing blood levels of GSK2586881 and RAS peptide responses throughout the duration of the hypoxia challenges.

The study will be placebo controlled (saline) so each subject can be used as their own control.

4.5. Dose Justification

GSK2586881 has been studied in 21 healthy subjects as single, intravenous doses over 30 minutes from 0.1 mg/kg to 1.2 mg/kg, and in repeated daily doses for up to six days of 0.4 mg/kg once a day. In addition, ARDS patients have received four doses of GSK2586881: 0.1 mg/kg, 0.2 mg/kg, 0.4 mg/kg and 0.8 mg/kg over a 24 hour period (n=5) or 0.4 mg/kg BID twice daily for 3 days (n=19). In a concluded investigator-sponsored study in Pulmonary Arterial Hypertension (PAH) (Study 204696), 5 subjects have received a single dose of either 0.2 mg/kg or 0.4 mg/kg. There were no SAEs associated with the infusion of GSK2586881 or reported within the 2-week period of study observation. There were no clinically significant changes in laboratory or vital signs measurements for any subject.

A population PK model for GSK2586881 was derived from data obtained in healthy subjects and ARDS patients and showed that the systemic PK profile was adequately described by a two-compartment first order elimination model and that the PK profile was independent of population (healthy subjects or ARDS patients). Furthermore the PK/PD response (AngII) in healthy subjects and ARDS patients was consistent with a single direct Emax model after accounting for differences in baseline AngII concentrations between healthy subjects and ARDS patients.

Based on the population PK/PD model described above, single intravenous doses of 0.4–1.2 mg/kg GSK2586881 are predicted to reduce elevated levels of AngII (baseline AngII consistent with an ARDS population) to levels consistent with that observed in healthy subjects for the duration of the hypoxic challenge (approx 2.25 h). The dose of 0.8 mg/kg has been selected to ensure maximal reduction of AngII levels, whilst maintaining dosing volumes within acceptable limits, and will further aid the understanding of the PK/PD relationship for GSK2586881.

4.6. Benefit:Risk Assessment

Summaries of findings from both clinical and non-clinical studies conducted with GSK2586881 can be found in the Investigator's Brochure (GlaxoSmithKline Document Number [2010N108777_04](#), 2017). The following section outlines the risk assessment and mitigation strategy for this protocol:

4.6.1. Risk Assessment

Potential Risk of Clinical Significance	Summary of Data/Rationale for Risk	Mitigation Strategy
Investigational Product (IP) [GSK2586881]		
Cardiovascular risk	During preclinical testing a brief period of non-sustained ventricular tachycardia was observed in one monkey receiving a dose of 20.8 mg/kg/day.	The dose used in this study is much lower and well below the No observed adverse effect level (NOAEL) for the 14 day repeat dose cynomolgus monkeys of 8 mg/kg/day.
Potential Reproductive/embryofetal risks	Preclinical studies have not been performed.	Women of childbearing potential will be excluded from the study.
Potential for Immunogenicity	There has been no induction of an immune response to rhACE2 in either of the clinical studies to date in healthy subjects or participants with ARDS.	Patients will have routine monitoring of any immunological response that may occur. If an immunological response is seen the patient will be asked to return for further monitoring and assessment(s).
Potential for rash	In study ACE114622, rash was reported more frequently in subjects receiving GSK2586881, although only one event was considered drug-related.	Patients will be monitored for rash in the clinical trials.

Potential Risk of Clinical Significance	Summary of Data/Rationale for Risk	Mitigation Strategy
Study Procedures		
Effects of hypoxia to study subjects (light headiness, headaches, nausea)	The subjects will be exposed to hypoxic conditions for approximately 80 minutes with a simulated altitude of 5000 m.	The subjects will be continuously observed and monitored with telemetry and pulse oximetry. Stopping criteria are included in the protocol.
Effects of hypoxia to staff at the clinical unit (light headiness, headaches, nausea)	Clinical site staff performing the assessments within the hypoxia chamber will potentially be exposed to hypoxic conditions with a simulated altitude of 5000 m.	All clinical staff entering the hypoxia chamber will be provided with an ambulatory oxygen supply.

4.6.2. Benefit Assessment

There will be no intended therapeutic clinical benefit to the subjects taking part in the study as it is a healthy volunteer study. However, subjects will undergo a medical evaluation during screening including physical exams, ECGs and laboratory assessments which may provide important health information.

By taking part in this study, the subject will be contributing to the development of GSK2586881 for the treatment of pulmonary hypertension and ARDS.

4.6.3. Overall Benefit:Risk Conclusion

The design of the study is considered low risk to the subjects and justified based on the work carried out by other researchers, the safety information from the nonclinical studies and the two previous clinical trials carried out on GSK2586881.

5. SELECTION OF STUDY POPULATION AND WITHDRAWAL CRITERIA

Specific information regarding warnings, precautions, contraindications, adverse events, and other pertinent information on the GSK investigational product or other study treatment that may impact subject eligibility is provided in the IB.

Deviations from inclusion and exclusion criteria are not allowed because they can potentially jeopardize the scientific integrity of the study, regulatory acceptability or subject safety. Therefore, adherence to the criteria as specified in the protocol is essential.

5.1. Inclusion Criteria

A subject will be eligible for inclusion in this study only if all of the following criteria apply:

AGE
1. Between 18 and 40 years of age inclusive, at the time of signing the informed consent.
TYPE OF SUBJECT
2. Healthy as determined by the investigator or medically qualified designee based on a medical evaluation including medical history, physical examination, spirometry, laboratory tests and cardiac monitoring. A subject with a clinical abnormality or laboratory parameter(s) which is/are not specifically listed in the inclusion or exclusion criteria, outside the reference range for the population being studied may be included only if the investigator (in consultation with the Medical Monitor if required) agree and document that the finding is unlikely to introduce additional risk factors and will not interfere with the study procedures. Note: Screened subjects with laboratory values outside of the normal range may be

TYPE OF SUBJECT

repeated once for inclusion into the study at the discretion of the Investigator.
 
3. Screening echocardiogram of good quality, without clinically significant abnormalities, and with mild-moderate tricuspid regurgitation sufficient for the reliable estimation of PASP, as determined by the echocardiography core laboratory or responsible cardiologist.
 
Screening PASP within the normal range according to site standards.
 
4. Subjects have not resided at an altitude >1500 m for more than 7 days in the last 4 months.
 
5. Able to complete all study procedures.
 
6. Any contraindication (orthopaedic, cardiac etc.) to perform exercise on a bicycle ergometer.

WEIGHT
7. Body weight 50–100 kg (inclusive).

SEX

8. Male or female (non child bearing potential)
 
Male subjects with female partners of child bearing potential must comply with the following contraception requirements from the time of first dose of study medication until at least five half-lives of study medication OR for a cycle of spermatogenesis following five terminal half-lives after the last dose of study medication.
 
a. Vasectomy with documentation of azoospermia.
 
b. Male condom plus partner use of one of the contraceptive options below:
 
 • Contraceptive subdermal implant • Intrauterine device or intrauterine system • Oral Contraceptive, either combined or progestogen alone [Hatcher, 2007a] • Injectable progestogen [Hatcher, 2007a] • Contraceptive vaginal ring [Hatcher, 2007a] • Percutaneous contraceptive patches [Hatcher, 2007a] 
This is an all-inclusive list of those methods that meet the following GSK definition of highly effective: having a failure rate of less than 1% per year when used consistently and correctly and, when applicable, in accordance with the product label. For non-product methods (e.g. male sterility), the investigator determines what is consistent and correct use. The GSK definition is based on the definition provided by the International Conference on Harmonization (ICH) [ICH M3 (R2), 2009].
 
The investigator is responsible for ensuring that subjects understand how to properly use

SEX

these methods of contraception.

Females:

A female subject is eligible to participate if she is not pregnant (as confirmed by a negative urine human chorionic gonadotrophin (hCG) test), not lactating, and the following condition applies:

Non-reproductive potential defined as:

- Pre-menopausal females with one of the following:
 - Documented tubal ligation
 - Documented hysteroscopic tubal occlusion procedure with follow-up confirmation of bilateral tubal occlusion
 - Hysterectomy
 - Documented Bilateral Oophorectomy
- Postmenopausal defined as 12 months of spontaneous amenorrhea [in questionable cases a blood sample with simultaneous follicle stimulating hormone (FSH) and estradiol levels consistent with menopause (refer to laboratory reference ranges for confirmatory levels)]. Females on hormone replacement therapy (HRT) and whose menopausal status is in doubt will be required to use one of the highly effective contraception methods if they wish to continue their HRT during the study. Otherwise, they must discontinue HRT to allow confirmation of post-menopausal status prior to study enrolment.

INFORMED CONSENT

9. Capable of giving signed informed consent as described in Section 7.2, which includes compliance with the requirements and restrictions listed in the consent form and in this protocol.

5.2. Exclusion Criteria

A subject will not be eligible for inclusion in this study if any of the following criteria apply:

CONCURRENT CONDITIONS/MEDICAL HISTORY (INCLUDES LIVER FUNCTION AND QTc INTERVAL)

1. ALT >1.5x Upper limit of normal (ULN).
2. Bilirubin >1.5xULN (isolated bilirubin >1.5xULN is acceptable if bilirubin is fractionated and direct bilirubin <35%).
3. Current or chronic history of liver disease, or known hepatic or biliary abnormalities (with the exception of Gilbert's syndrome or asymptomatic gallstones).

CONCURRENT CONDITIONS/MEDICAL HISTORY (INCLUDES LIVER FUNCTION AND QTc INTERVAL)

4. Prior history of altitude sickness.
5. Recently been scuba diving (within 1 week before screening).
6. QTc > 450 msec

NOTES:

- The QTc is the QT interval corrected for heart rate according to Bazett's formula (QTcB), Fridericia's formula (QTcF), and/or another method, machine-read or manually over-read.
- The specific formula that will be used to determine eligibility and discontinuation for an individual subject should be determined prior to initiation of the study. In other words, several different formulae cannot be used to calculate the QTc for an individual subject and then the lowest QTc value used to include or discontinue the subject from the trial.
- For purposes of data analysis, QTcB, QTcF, another QT correction formula, or a composite of available values of QTc will be used as specified in the Reporting and Analysis Plan (RAP).

CONCOMITANT MEDICATIONS

7. Unable to refrain from prescription or non-prescription drugs, including agents active in the central nervous system, vitamins, herbal and dietary supplements (including St John's Wort) within 7 days (or 14 days if the drug is a potential enzyme inducer) or 5 half-lives (whichever is longer) prior to the first dose of study medication and throughout the study, unless in the opinion of the Investigator and/or GSK Medical Monitor (if needed) the medication will not interfere with the study procedures or compromise subject safety.

RELEVANT HABITS

8. History of regular alcohol consumption within 6 months of the study defined as:
 - An average weekly intake of >21 units for males or >14 units for females. One unit is equivalent to 8 g of alcohol: a half-pint (~240 mL) of beer, 1 glass (125 mL) of wine or 1 (25 mL) measure of spirits.
9. Urinary cotinine levels indicative of smoking or history or regular use of tobacco- or nicotine-containing products within 6 months prior to screening.

CONTRAINdications

10. History of sensitivity to any of the study medications, or components thereof or a history of drug or other allergy that, in the opinion of the investigator or Medical Monitor, contraindicates their participation.

DIAGNOSTIC ASSESSMENTS AND OTHER CRITERIA

11. Presence of hepatitis B surface antigen (HBsAg), positive hepatitis C antibody test result at screening or within 3 months prior to first dose of study treatment. For potent immunosuppressive agents, subjects with presence of hepatitis B core antibody (HBcAb) should also be excluded.
12. A positive pre-study drug/alcohol screen.
13. A positive test for HIV antibody.
14. Where participation in the study would result in donation of blood or blood products in excess of 500 mL within 56 days.
15. The subject has participated in a clinical trial and has received an investigational product within the following time period prior to the first dosing day in the current study: 30 days, 5 half-lives or twice the duration of the biological effect of the investigational product (whichever is longer).
16. Exposure to more than four new chemical entities within 12 months prior to the first dosing day.

5.3. Screening/Baseline/Run-in Failures

Screen failures are defined as subjects who consent to participate in the clinical trial but are never subsequently randomised. In order to ensure transparent reporting of screen failure subjects, meet the Consolidated Standards of Reporting Trials (CONSORT) publishing requirements, and respond to queries from Regulatory authorities, a minimal set of screen failure information is required including Demography, Screen Failure details, Eligibility Criteria, and Serious Adverse Events (Section 7.2.1.4).

Subjects that are not enrolled into the study within the allotted screening window may be re-screened once. If re-screening is performed, subjects are assigned a different unique subject Identification (ID) number for the re-screening, and all screening procedures must be repeated.

See the Study Reference Manual (SRM) for specific details.

5.4. Withdrawal/Stopping Criteria

Subjects may be withdrawn from the study for any of the following reasons:

- A subject may withdraw from study treatment at any time at his/her own request, or may be withdrawn at any time at the discretion of the investigator for safety, behavioural or administrative reasons. If a subject withdraws from the study, he/she may request destruction of any samples taken, and the investigator must document this in the site study records.
- If a subject's oxygen saturation falls below 60% (persistently for >15 seconds) at any point during the hypoxia challenge.

- If the subject experiences worsening shortness of breath or other symptoms, which in the opinion of the investigator are consistent with altitude sickness.
- The Sponsor may request a subject withdraw for reasons such as significant protocol deviations (after discussion with the investigator).
- Study is terminated by the Sponsor.

A subject will be considered to have prematurely withdrawn from the investigational product if they do not complete all doses in the treatment phase having received the first dose of investigational product, for any reason.

Once a subject has discontinued investigational product the subject may not re-enter the study. Dosing of the subjects with the investigational product may be stopped at any time, at the request of the subject or at the discretion of the Investigator (i.e. if clinically significant adverse events should occur). Withdrawal due to adverse events will be distinguished from withdrawal for other reasons.

If a subject decides to withdraw or is withdrawn by the Investigator, the reasons for withdrawal and the results of any relevant tests will be recorded in the Case Report Form (CRF) and the planned follow-up procedures will be performed, where possible.

The following actions must be taken in relation to a subject who fails to attend the clinic for a required study visit:

- The site must attempt to contact the subject and re-schedule the missed visit as soon as possible.
- The site must counsel the subject on the importance of maintaining the assigned visit schedule and ascertain whether or not the subject wishes to and/or should continue in the study.
- In cases where the subject is deemed 'lost to follow up', the investigator or designee must make every effort to regain contact with the subject (where possible, 3 telephone calls and if necessary a certified letter to the subject's last known mailing address or local equivalent methods). These contact attempts should be documented in the subject's medical record.
- Should the subject continue to be unreachable, only then will he/she be considered to have withdrawn from the study with a primary reason of "Lost to Follow-up".

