- It is anticipated that increasing the altitude of the chamber from 4000 to 5000 m will reduce oxygen saturation to as low as 65% in some subjects (when concurrently exercising). Therefore, the current individual subject withdrawal criteria of oxygen saturation falling *below 65% during the hypoxia challenge* (see Section 5.4) will be reduced to *below 60%* and a timeframe for the reduction added (persistently for >15 seconds). This is justified, because subjects will be continually monitored during the

challenge, and immediately removed from the chamber should oxygen saturation decline to the withdrawal limit. Oxygen saturation recovery on returning to normoxia is very rapid.

- The exercise challenge in Part 2 will be modified. In Part 1 of the study, PASP data at the T3 time-point were extremely variable. Review of the literature shows that any exercise-induced increase in PASP will decline to baseline extremely rapidly following cessation of exercise ([Argiento](#), 2010). This likely explains the unreliability of data at T3. In Part 2, the exercise challenge will be conducted on a semi-recumbent ergometer, allowing acquisition of echo recordings during (rather than after) exercise. The workload of the exercise challenge will be reduced (from 70% VO₂max to 50% VO₂max), because of the increase in chamber altitude. Additionally, echo recordings will be taken within 2 minutes of starting exercise, rather than after exercise, based on reports that prolonged steady state exercise can conversely decrease pulmonary vascular pressures, due to a reduction in pulmonary blood volume as the systemic circulation adapts ([Naeije](#), 2018).
- In Part 2 of the study, at all time-points, the protocol for echo recordings will be modified with the aim of improving data quality and reliability. The following changes will be made: calculation of PASP (outlined in Section [7.4](#)) will be conducted *after* image acquisition (rather than *during* the recording); the sonographer will aim to capture at least 5 good quality images to estimate PASP; and a physician ‘over-reader’ process will be introduced. PASP will be calculated by a primary reader (the sonographer) and all echo images/calculations will be reviewed by a suitably qualified physician, who will provide a quality statement.
- In Part 2 of the study, an exploratory echo endpoint has been added, which will allow estimation of pulmonary vascular resistance (PVR).

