Echocardiogram	X	X			X		X ^{6 below}		X				
Subject enters chamber					X							Subject enters chamber approximately 30 min after study treatment	
Study Treatment (Dosing)		X											
Subject leaves chamber							X					Subject leaves chamber after the fourth echocardiogram, blood samples and vital signs have been taken.	
Exercise challenge						X						Part 1: exercise at 70% VO ₂ max for ~5-10 min. Echo conducted immediately after. Part 2: exercise at 50% VO ₂ max for 2 min. Echo started at 2 min into the challenge, and the subject continues exercising.	
Ventilatory parameters	X	X			X				X			Measurements to be taken 2 min before echocardiograms.	

Procedure	Treatment Period 1 and 2 (Washout 3-14 days)											Notes	
	Times relative to start of dosing				Hypoxic Challenge ~80 min (Times relative to entry to Chamber)								
	Pre-dose	0h	15 min	15-45 min	0-60 min	60 min	60-70 min	Immediately after exercise	On exit from chamber	After 30 min rest	60 min after exit from Chamber		
Pulse Oximetry (O ₂ saturation)	←-----→											Will be continuously monitored for safety. A measurement should be recorded at the time of each echocardiogram and databased. Part 2: when the echo is recorded during the exercise challenge, pulse oximetry will be recorded immediately prior to initiation of the echo at 2 minutes into exercise.	
Telemetry	←-----→											Will be continuously monitored for safety.	
RAS Biomarkers	X	X ¹	X ²	X ³		X ²		X ²	X ⁴	X ²			
SP-D	X	X ¹	X ²	X ³		X ²		X ²	X ⁴	X ²			
PK sampling	X	X ¹	X ²	X ³		X ²		X ²	X ⁴	X ²			
AE/SAE review		←-----→											
Concomitant medication review	X												

1. Take at the end of the infusion
2. Taken immediately after echocardiogram
3. Immediately before entering the chamber
4. To be taken as soon as possible after leaving chamber
5. On this occasion ONLY, vital signs to be taken after the blood draw.
6. In Part 2, echo at this time-point taken 2 minutes into the exercise challenge (not immediately after exercise).

After written informed consent, screening assessments will be performed as outlined in the Time and Events Table (Section 7.1).

The following demographic parameters will be captured: year of birth, sex, race and ethnicity.

Medical/medication/family history will be assessed as related to the inclusion/exclusion criteria listed in Section 5.

Cardiovascular medical history/risk factors (as detailed in the CRF) will be assessed at screening.

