7.7. Pulse Oximetry

Oxygen saturation will be monitored continuously via pulse oximetry as detailed in the SRM. Measurements will be taken at the same time as the echocardiograms and recorded in the eCRF.

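### Part 2 saturation: a subject removed at the 60% limit before the 2-minute exercise reading has no scheduled T3 value, so the T3 comparison can understate a drug-related drop (probably by little)

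*Protocol*

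**What the plan says.** Five rules meet here, all in the protocol.

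- **Removal.** Section 5.4 opens "Subjects may be withdrawn from the study for any of the following reasons" and lists the case where a subject's "oxygen saturation falls below 60% (persistently for >15 seconds) at any point during the hypoxia challenge". Section 2.1.1, which justifies the lower limit, says subjects are monitored continually and "immediately removed from the chamber should oxygen saturation decline to the withdrawal limit".
- **Recording.** The treatment-period time and events table (7.1.2) says "A measurement should be recorded at the time of each echocardiogram and databased", and for the Part 2 exercise echo "pulse oximetry will be recorded immediately prior to initiation of the echo at 2 minutes into exercise". Section 7.7 agrees: "Measurements will be taken at the same time as the echocardiograms and recorded in the eCRF".
- **Use of the value.** Section 9.1 gives a rule of thumb for success that also requires a small probability of a treatment-related absolute saturation reduction above 5%. The synopsis has saturation analysed in a similar way to PASP. Section 9.3.2.2 names T0 and T3 as the critical saturation time points for the Part 2 reviews.
- **Records on withdrawal.** Under section 5.4, the reasons and "the results of any relevant tests will be recorded in the Case Report Form (CRF").
- **Numbers.** Up to 14 subjects enter Part 2, and withdrawn subjects are not replaced (4.3).

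On expected levels, section 2.1.1 says that 5000 m "will reduce oxygen saturation to as low as 65% in some subjects (when concurrently exercising").

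**The concern.** The removal rule acts on the same variable that the comparison judges. If the drug lowers saturation, more subjects reach the limit on drug than on placebo, and the readings that disappear are the lowest ones. The remaining T3 values then show a smaller difference than the true one.

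This matters because section 2.1 makes the effect on oxygen saturation part of the study's main goals and says that accentuated desaturation would call for caution in acute lung injury. In most comparisons, lost data cost precision or bias the result in an unknown direction. Here the direction is known: the drug looks safer. The Part 2 reviews are triggered by subjects who completed both periods, so a removed subject does not bring a review closer either.

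**Working it through.** The protocol gives no figure for saturation precision or expected removals, so there is nothing of its own to reproduce. It also gives no SD or within-subject correlation for saturation. I assume a normal T3 saturation, SD 3, 5 or 7 points, correlation 0.3 or 0.6, and a true drug drop of 5 points.

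**1. When is T3 lost?** Only when the sustained fall below 60% leads to removal before the 2-minute reading. A fall that begins after the reading, or less than 15 seconds before it, leaves T3 intact. Losing every value below 60% is therefore a worst case; I also take a random half lost.

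**2. Size under the protocol's own expectation.** Read the expected 65% as the lowest of 14 placebo values. The expected minimum of 14 normal values lies 1.70 SD below the mean.

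- Placebo mean = 65 + 1.70 × SD = 70.1, 73.5 and 76.9% for SD 3, 5 and 7.
- Drug mean = placebo mean − 5 = 60 + 1.70 × SD.
- Share of drug readings below 60% = Φ(−1.70) = about 4.4% for every SD, or 14 × 0.044 = 0.6 of a subject.

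If all values below 60% are lost and all remaining values are used, the estimated drop is 5 − λ(drug) + λ(placebo), with λ = SD × φ(z) / (1 − Φ(z)) and z = (60 − mean) / SD:

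- SD 3: 5 − 0.29 + 0.00 = 4.7
- SD 5: 5 − 0.49 + 0.05 = 4.6
- SD 7: 5 − 0.68 + 0.15 = 4.5

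Simulated complete pairs give 4.6 to 4.9. With a random half lost, the results are 4.7 to 4.9 (all values) and 4.8 to 4.9 (pairs). The shortfall is about 0.1 to 0.5 points.

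**3. Size if saturation runs nearer 60%.** Complete pairs, true drop 5, ranges over SD and correlation. The last column simulates 14 subjects with the altitude step-down of section 7.3.2, assuming a gain of 2 to 5 points per 500 m and a count that restarts after each cut.

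| Assumed placebo mean | Placebo values below 65% | All below 60% lost | Half lost | All lost, with step-down |
|---|---|---|---|---|
| 67% | 25–39% | 3.2–4.5 | 4.5–4.8 | 3.5–4.7 |
| 70% | 5–24% | 3.7–4.9 | 4.5–4.9 | 3.8–4.9 |
| 75% | 0–8% | 4.4–5.0 | 4.7–5.0 | 4.4–5.0 |

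**4. Effect on the rule of thumb.** Take 14 subjects, SD 5, correlation 0.6, a flat-prior t posterior on complete pairs, and call a posterior probability below 0.2 small, since section 9.1 sets no limit. With a true drop of exactly 5 and full data, the posterior is small in 20% of trials. With every value below 60% lost and no step-down, this becomes 23–25% at means of 75–73.5% and 33–43% at 70–67%. With step-down (gain 3) it is 22% (75%), 31% (70%) and 38% (67%). With a true drop of 7.5 and step-down it stays at 0–4%.

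**5. Does the planned model repair it?** Section 9.4 specifies an unstructured covariance within period, so the earlier time points can inform a missing T3, but only under missing at random. I regressed T3 on T2 within each period, for a true drop of 7, mean 70%, SD 6 and all values below 60% lost. The unadjusted estimate is 4.6. Adjusted, it is 4.7, 5.3 and 6.1 for T2–T3 correlations of 0.3, 0.7 and 0.9. Part of the loss is recovered, never all of it.

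**6. Does left-censoring repair it?** A bivariate normal likelihood censored at 60%, with Period 2 missing after a Period 1 removal, gives mean estimates of 4.9 to 5.1 for a true drop of 5 with 14 subjects.

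**The case against.** Much of the opposing case stands.

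- **Assignment by events.** Section 9.4 assigns saturation to T0–T4 by where it falls in the sequence of events, and section 5.4 sends relevant test results to the CRF. A removal reading taken during exercise could arguably be placed at T3. This weakens the point but does not close it: no text requires the value and time at removal to be recorded, and a reading below the limit shows only that saturation had fallen at least that far.
- **Room for the analysis plan.** Section 9.4 leaves details of other endpoints to the reporting and analysis plan, which may handle this. But that plan cannot use a reading that was never captured.
- **A soft condition.** Section 9.1 is a rule of thumb that sets no limit for small and names no saturation time point. T3 is inferred from the synopsis and section 9.3.2.
- **Removals stay visible.** They count towards the altitude step-down, and saturation and adverse events are reviewed by a sponsor-open team. A reader might infer that a harmful drop would pass unnoticed; the documents do not support that.
- **Screening.** Part 2 candidates face a 10-minute tolerance test at 5000 m followed by incremental exercise. The simulations do not model this, and it should reduce removals.

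A reader might also see a contradiction between withdrawal that may happen (5.4) and removal that is immediate (2.1.1). There is none: the first concerns leaving the study, the second leaving the chamber. It does mean that loss of Period 2 is possible rather than certain.

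**Conclusion.** The point holds as a minor one. The removal rule, the single exercise reading and a model that relies on missing at random together let the T3 saturation comparison understate a drug-related drop. The direction is firm; the size is not. Under the protocol's expectation for 5000 m, the understatement is about 0.1 to 0.5 points for a true drop of 5. It grows beyond that only if Part 2 saturation runs closer to 60%, and the decision is then affected mainly when the true drop is near the 5-point threshold.

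A reader might take the 63.5% mean of the cited hypoxia-and-exercise study (Appendix 6, Amendment 03) as the Part 2 level and infer a large bias. The protocol does not support that: such a mean would put 58–69% of placebo values below 65%, which does not fit a level expected only in some subjects.

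All sizes rest on assumed SD, correlation, mean and timing of removals.

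**What to change.** 1. In 7.1.2 and 7.7, require the saturation value and time at removal to be entered in the eCRF.
2. In 9.4, state that a removal at the limit during the challenge and before T3 enters the T3 saturation analysis as a value at or below the removal reading (left-censored), at least as a sensitivity analysis for the section 9.1 condition.
3. Tabulate such removals by treatment at each Part 2 review.

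The cost is one eCRF entry, a sentence in 9.4 and a small table. No procedures or subjects are added, because saturation is already monitored continuously. The downside is a slightly more complex saturation model that leans on a distributional assumption, which 14 subjects cannot test well.
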